2.1 Intent-to-treat population

The intent-to-treat (ITT) population will include all patients who participated in this trial after randomization, and will be grouped based on the treatment they were randomized to receive.

2.2 Per-protocol population

The per-protocol (PP) population will consist of patients who participated in this trial and fully complied with the protocol, and will be used for sensitivity analysis.

2.3 The as-treated (AT) population will consist of patients who received the actual surgical procedure, and will be used for sensitivity analysis.

2.4 Safety population

The safety population will consist of all randomized patients in this trial, excluding those who withdrew prior to the surgery. Patients will be grouped according to the treatment they actually received, and safety monitoring will be conducted on this population.

3 Data validation

Upon data entry, the database will validate data in real time based on pre-programmed validation rules. Each participating center will have a data manager who verifies the completeness, consistency, and timeliness of all data. For missing data, the data manager is also responsible for retrieving the original data, with a high likelihood of successful retrieval. Additionally,

the data manager will check and track data related to primary and key secondary outcomes at specified time points.

4 Data Analysis

4.1 General calculations

For the summary of population characteristics, all percentages will be calculated with the total number of the intent-to-treat (ITT) population as the denominator (including all patients with missing data for the relevant variable). For the summary of categorical outcome variables (e.g., complication rate), patients with missing data will be excluded from the denominator when calculating percentages. For the summary of continuous outcome variables (e.g., estimated blood loss, length of hospital stay, cost), patients with missing data will be excluded when calculating means or medians. When patients with missing data are excluded from the denominator, the number of patients included in the summary will be clearly reported.

All percentages, means, standard deviations (SDs), medians, interquartile ranges (IQRs), and ranges will be rounded to 1 or 2 decimal place. P-values will be rounded to 3 decimal places. Parameter estimates, standard errors (SEs), relative ratios (RRs), and 95% confidence intervals (CIs) will be reported to 1 or 2 decimal places. Hypothesis testing for

primary outcome will be one-sided at the 2.5% significance level, others will be two-sided at the 5% significance level.

4.2 Screening data

The CONSORT flow diagram will be used to summarize the progress of participants throughout the study. Participating sites are required to record details of all randomized participants, including those who no longer meet the eligibility criteria or do not undergo surgery. Protocol violations will also be summarized, along with the reasons for each deviation.

4.3 Withdrawals

The number of participants who withdraw consent from the study will be summarized, along with the reasons for their withdrawal. For patients who withdraw prior to surgery, no further data submission will be required. For those who withdraw after surgery, collection of treatment and follow-up data will still be required (including the administration of additional patient-reported questionnaires), but patients will not receive any further trial-specific interventions. With patients' permission, data collected before withdrawal may still be used for analysis. If a patient explicitly states that they do not wish to contribute further data to the trial, their wishes will be respected, and the patient will be handled as a censored case.

4.4 Baseline characteristics

Baseline clinical data, as documented in the baseline assessment forms, will be tabulated using frequencies and summary statistics for each treatment group and the overall population. No statistical testing will be performed on these data.

4.5 Primary outcome

The primary endpoint will be analyzed in the ITT population and defined as the rate of severe complications (Clavien-Dindo grade \geq III) within 90 days post-surgery, the primary endpoint will be assessed as follows (Time Frame: For the Study Group, from the SDT to 90 days after surgery; if the patient undergoes ileostomy as a salvage procedure, the time frame will be extended to 90 days after stoma reversal. For the Control Group, from ileostomy creation to 90 days after stoma reversal. For patients in both groups who do not undergo stoma reversal, the time frame will be defined as 90 days after the initial surgery). This endpoint will be analyzed using logistic regression to calculate the relative ratio (RR), with reporting of the between-group difference and corresponding 95% confidence interval (CI).

Subgroup analysis will be performed according to: Age, Gender, Body mass index, Use of neoadjuvant radiotherapy, Tumor to anal verge, Multiple high-risk factors, Pathological T stage, Pathological N stage,

Presence of prior abdominal surgery. The RRs will be reported with corresponding 95% CI.

4.6 Secondary outcomes

Secondary outcomes will be analyzed in the ITT population. For categorical variables, a two-sided Pearson's χ^2 test or Fisher's exact test will be used, as appropriate; the rate difference and corresponding 95% CI will be calculated using the Miettinen-Nurminen method. For continuous variables, Student's t-test (for normally distributed data) or the Mann-Whitney U test (for non-normally distributed data) will be applied, as appropriate; the median difference and corresponding 95% CI.

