Statistical Analysis Plan (Final, Version 1.2)

Principal Investigator: [name]

Research Institution: Sir Run Run Shaw Hospital, Zhejiang University

Register Number: NCT06204497

Date: 2025-10-26

Version: 1.2

Statistical Analysis Plan Authors: [name]

Department of Epidemiology and Biostatistics, Zhejiang University

School of Medicine, China

E-mail: [contact]

1. Introduction

This trial is a multicenter, prospective, randomized, controlled, open label, parallel-group, non-inferiority trial to evaluate the safety and efficacy of stent-based diverting technique (SDT) versus ileostomy in rectal cancer patients. In this trial, SDT is considered to reduce the overall length of post-operation hospital stay and medical costs, improve patients' quality of life, while not increasing the peri-operative complication rate. The primary outcome was the 90-day incidence of severe complications (Clavien-Dindo grade \geq III). Secondary outcomes included overall complication rate, anastomotic leakage rate (grade B/C), length of postoperative hospital stay, hospitalization costs, and 90-day postoperative quality of life.

Patients were randomized 1:1 to two groups:

- SDT group: rectal cancer surgery plus stent-based diverting technique
- Ileostomy group: rectal cancer surgery plus protective ileostomy

Follow-up concluded 90 days after the last patient underwent surgery.

2. Population

● 2.1 Intent-to-treat population

The intent-to-treat (ITT) population will include all randomized participants, with grouping according to their originally assigned treatment,

regardless of whether the allocated intervention was actually received or completed. Primary and secondary outcome analyses will be performed in the intent-to-treat (ITT) population. As randomization was performed intraoperatively, a modified ITT (mITT) population was not defined in this study.

- **2.2 Per-protocol population**

The per-protocol (PP) population includes all randomized participants who completed the study as planned, with no major protocol violations, adequate adherence to the assigned intervention, and sufficient follow-up data for the primary outcome assessment. Primary and secondary outcome analyses will be conducted in the PP population as sensitivity analyses.

- **2.3 As-treated population**

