4.2 General calculations

For the summary of population characteristics, all percentages will be calculated with the total number of the intent-to-treat (ITT) population as the denominator (including all patients with missing data for the relevant variable). For the summary of categorical outcome variables (e.g., complication rate), patients with missing data will be excluded from the denominator when calculating percentages. For the summary of continuous outcome variables (e.g., estimated blood loss, length of hospital stay, cost), patients with missing data will be excluded when calculating means or medians. When patients with missing data are excluded from the denominator, the number of patients included in the summary will be clearly reported.

All percentages, means, standard deviations (SDs), medians, interquartile ranges (IQRs), and ranges will be rounded to 2 decimal place. P-values will be rounded to 3 decimal places. Parameter estimates, standard errors (SEs), relative ratios (RRs), and 95% confidence intervals (CIs) will be reported to 2 decimal places. The primary outcome will be performed one-sided at $\alpha = 0.025$, with results presented as treatment differences and corresponding 97.5% one-sided confidence intervals. Other comparisons will be two-sided at $\alpha = 0.05$, with 95% two-sided confidence intervals reported.

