4.3 Missing data

For missing baseline data (age, BMI, etc.), multiple imputation by chained equations (MICE) will be used. The number of imputed datasets, imputation variables, and diagnostic checks will be fully documented. For quality of life (QoL) data with missing values, only observed cases will be included in the analysis (missing values excluded from denominator). For crossover or treatment-switching patients, the ITT principle will be strictly maintained in the primary analysis; treatment switching will be summarized descriptively and explored in the as-treated sensitivity analysis. For protocol deviations, all major violations will be listed by center and patient, with impact on the primary outcome assessed in PP and AT analyses.

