4.7 Secondary outcomes

Secondary outcomes will be analyzed in the ITT population. Continuous variables (e.g., operation time, estimated blood loss, distance from anastomosis to anal verge, length of postoperative hospital stay, hospitalization cost, quality of life score) will be compared using the Student's t-test (for normally distributed data) or Wilcoxon rank-sum test (for non-normally distributed data), with the median difference and corresponding 95% confidence interval reported. For categorical variables (e.g., surgical approach, surgical type, anastomotic technique, overall/mild/severe complication rate, Clavien-Dindo grade), the two-

sided Pearson's χ^2 test or Fisher's exact test will be used as appropriate (see appendix Table 4).

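### The planned tests for postoperative stay and hospitalization cost ignore centre, which costs precision in the ITT comparison and leaves the non-randomised comparisons open to differences in centre mix

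*SAP*

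**What the plan says.** The design is stated in section 1 of V1.2: "This trial is a multicenter, prospective, randomized, controlled, open label, parallel-group, non-inferiority trial". Allocation is equal: "Patients were randomized 1:1 to two groups".

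Section 4.7 of V1.2 analyses secondary outcomes in the ITT population. Its list of continuous variables includes "length of postoperative hospital stay, hospitalization cost, quality of life score", and these "will be compared using the Student's t-test (for normally distributed data) or Wilcoxon rank-sum test", with a median difference and 95% CI. Section 4.2 sets the level: "Other comparisons will be two-sided at $\alpha = 0.05$, with 95% two-sided confidence intervals reported". V1.1, which is bound in the same file and superseded, has the same pair of tests in its section 4.6 ("For continuous variables, Student's t-test (for normally distributed data) or the Mann-Whitney U test (for non-normally distributed data) will be applied"). Mann-Whitney U and Wilcoxon rank-sum are the same test, so the choice survived the revision.

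Centre appears elsewhere in V1.2. Section 4.6 defines a subgroup by centre volume (at least 50 cases versus fewer), and section 4.3 says that "all major violations will be listed by center and patient". Centre must therefore be available for each patient. It enters an outcome comparison only through that subgroup, which is listed under the primary outcome.

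Section 4.8 carries the ITT methods over to the per-protocol (PP) and as-treated (AT) populations. The appendix table of stay and cost also has rows for total stay and total cost restricted to patients who had a reversal.

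**The concern.** Hospital cost and length of stay may well differ between hospitals through local prices and discharge routine. The SAP gives no figure for this, so it is an assumption, but a plausible one for a cost outcome in a multicentre trial. A two-sample test on pooled values puts all between-centre variation into the error term. The rank test also ranks patients of different hospitals against each other.

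These outcomes carry weight. Section 1 of V1.2 names shorter stay and lower cost among the expected benefits. Section 4.6 relies on them, with avoidance of a stoma and better quality of life, to call an absolute increase of up to 2.8 percentage points in severe complications acceptable. Evidence for those benefits should be as precise as the collected data allow.

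**Working it through.** **Inputs from the SAP.** 1:1 individual randomisation; ITT; two-sided 0.05; t-test or rank-sum test without a centre term. The SAP gives no SD, sample size, power, number of centres or between-centre variance for stay or cost. There is no planned figure to reproduce, and every size below rests on stated assumptions.

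**Step 1: interval width.** Let r be the share of outcome variance explained by centre. With centre in a linear model the residual variance falls by the factor (1 − r), so the unadjusted interval is 1/√(1 − r) times as wide as the adjusted one. This ignores the small loss from estimating the centre terms.

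**Step 2: power.** Assume a true difference d = 0.25 SD and n per arm. Power = Φ(d / (√(2/n) · √(1 − r)) − 1.96).

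- n = 200: d/√(2/n) = 0.25/0.1 = 2.5, so unadjusted power is Φ(0.54) = 70.5%.
- n = 400: 0.25/0.0707 = 3.54, so unadjusted power is Φ(1.58) = 94%.

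| Assumed r | Width ratio | Adjusted power, n = 200 | Adjusted power, n = 400 |
|---|---|---|---|
| 10% | 1.05 | 75.0% | 96% |
| 20% | 1.12 | 79.8% | 98% |
| 30% | 1.20 | 84.8% | 99% |
| 40% | 1.29 | 89.8% | over 99% |

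The width ratio does not depend on d or n; the power gain does, and it is small where power is already high.

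**Step 3: allocation balanced within centre.** The arm difference then varies less than the t-test assumes, by the factor (1 − r) in variance. Power of the planned test becomes Φ((2.5 − 1.96)/√(1 − r)) at n = 200: 71.5%, 72.7%, 74.1% and 75.7% for r = 10, 20, 30 and 40%. That is slightly above 70.5% but still below the adjusted model. The planned test is also conservative: its true two-sided error is 2Φ(−1.96/√(1 − r)), which at r = 30% is 2Φ(−2.343) = 0.019.

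**Step 4: false positives, by simulation.** Null data, two-sided 0.05, 2,500 runs per scenario. Assumed settings: 10 centres with 400 patients in total or 20 centres with 1,000, unequal centre sizes, and intraclass correlation (ICC, the same quantity as r) of 0.1, 0.3 or 0.5. A log-normal outcome was also run for 10 centres at ICC 0.3 and 0.5. The Monte Carlo standard error near 0.05 is √(0.05 × 0.95/2500) = 0.0044.

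| Randomisation | t-test and rank test, type I error |
|---|---|
| Not stratified by centre, ICC 0.1 to 0.5 | 0.046 to 0.057 |
| Balanced within centre, ICC 0.1 | about 0.04 to 0.05 |
| Balanced within centre, ICC 0.3 | 0.014 to 0.023 |
| Balanced within centre, ICC 0.5 | 0.010 to 0.014 |

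The centre-adjusted linear model gave 0.040 to 0.059 throughout. The planned tests are at nominal or below it, never materially above.

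**Step 5: cross-check of power.** At an effect giving 80% unadjusted power, the formula gives 84%, 92% and 98% with adjustment at ICC 0.1, 0.3 and 0.5. The simulated adjusted power was 82 to 84%, 91 to 92% and 97 to 98%.

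**Step 6: comparisons outside randomisation.** AT groups patients by the procedure received, PP drops patients after randomisation, and the reversal-only rows condition on a later event. If crossover, violations or reversal differ between centres, the arms can differ in centre mix systematically, and the planned tests would not remove that.

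**The case against.** A reader might infer that differences in local prices and discharge practice could pass for an effect of the stent technique. For the ITT comparison the documents do not support that. Patients are randomised 1:1, so centre mix is balanced in expectation, and chance imbalance is already inside the nominal 5%. Step 4 confirms it. If allocation was balanced within centre, the planned tests work against a claim for the stent technique.

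Other objections:

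- **Unadjusted two-sample tests are valid for secondary outcomes in a randomised trial.** True. Nothing in the SAP is miscalculated here; this is a point about efficiency.
- **The size is assumed.** True. The SAP gives neither d, n nor r. At n = 400 per arm the power argument nearly disappears. The control arm faces a second admission for reversal, so the true difference in total stay and cost could be far larger than 0.25 SD. The formula also describes a linear model and does not quantify the loss for the rank test.
- **Stratification by centre may be described in the protocol.** It may. The SAP is silent, and the point does not depend on it: without stratification precision is lost, and with it the intervals are also miscalibrated.
- **A linear model changes the effect measure.** True. Section 4.7 plans a median difference. However, the appendix table already lays out stay and cost as mean ± SD, so a mean difference fits the planned presentation.
- **It is late.** V1.2 is dated 2025-10-26 and section 1 describes follow-up as concluded, so any added model needs a clear label.

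What stands against these objections is the narrow point: centre is known, the tests ignore it, and using it needs no new data.

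**Conclusion.** The point holds as one of precision. Section 4.7 of V1.2 fixes tests for stay and cost that ignore centre. In ITT the cost is an interval about 1.05 to 1.29 times as wide as necessary if centre explains 10 to 40% of the variance, an assumed range. If allocation was balanced within centre, the intervals are also too wide for their stated coverage, with simulated type I error of 0.010 to 0.023 at ICC 0.3 to 0.5. There is no inflation of false positives in ITT, so the planned ITT tests remain valid.

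Bias from centre mix is a concern only for the PP, AT and reversal-only comparisons. There too it is a possibility, not something the SAP shows to be present. The change is worth making because it is cheap and because section 4.6 uses these outcomes to support the margin. No particular gain in power can be promised.

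**What to change.** In section 4.7 of V1.2:

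- For total stay and total cost, report a centre-adjusted mean difference with 95% CI from a linear model with treatment and centre, using robust or bootstrap standard errors.
- Where a rank test is kept, use the centre-stratified (van Elteren) version in place of the plain Wilcoxon test.
- State a rule, fixed without reference to outcomes by arm, for pooling very small centres.
- Apply the same analysis to the PP, AT and reversal-only comparisons, noting that it removes the part due to centre mix but no other selection.
- Say whether the mean difference stands beside the planned median difference or replaces it.

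If the data are already locked, keep the planned analysis and label the adjusted one as supplementary.

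The cost is SAP wording and a few lines of code, with no new data. The downsides are the pooling rule, a second or different effect measure, and a slight loss of degrees of freedom if centre turns out to explain almost nothing.

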4.7 Sensitivity analysis

Sensitivity analyses will be conducted for the per-protocol (PP) and as-treated (AT) populations. The statistical methods used in these sensitivity analyses will be consistent with those applied to the intent-to-treat (ITT) population. Results will be compared and interpreted across the ITT, and PP populations to determine whether protocol violations or missing data have an impact on the study outcomes.

5 Safety monitoring

Safety indicators will be monitored and analyzed in the safety population. Each participating medical center will designate independent monitors to

oversee safety indicators, including the postoperative severe complication rate and serious adverse events.

To ensure participant safety and trial rigor, an independent Data and Safety Monitoring Board (DSMB) was composed of a colorectal surgeon, a biostatistician, and an ethics consultant. The DSMB conducted blinded reviews (with no access to group allocation) of the primary outcome: the incidence of 90-day severe complications (Clavien-Dindo grade \geq III) and all serious adverse events (SAEs) every 6 months. During these reviews, no protocol violations or safety signals warranting trial suspension were identified, and the DSMB consistently recommended that the trial continue as planned.

Signature: [name]

A handwritten signature in black ink, appearing to be '[name]', enclosed in a light gray rectangular box.

Date: 2025-10-06

Summary of Statistical Analysis Plan amendments

Version	Section	Revision Content	Reason for Revision
V1.1	Sensitivity analysis	Add the as-treated analysis as the sensitivity analysis	To meet high-standard SAP requirements for crossover data
V1.2	Missing data	Specified multiple imputation (MICE) for baseline missing data; clarified observed-case analysis for QoL; standardized handling of crossover, protocol deviations, and center-specific violations	To meet high-standard SAP requirements for missing and crossover data
V1.2	Primary outcome	Unified primary analysis as risk difference (RD); non-inferiority based on RD with 97.5% one-sided CI	Ensure non-inferiority analysis is statistically correct
V1.2	Primary outcome	Added Relative risk (RR) estimation method: binomial regression with log-link, reported with two-sided 95% CI as supplementary measure	Clearly define RR analysis without interfering with non-inferiority testing
V1.2	Primary outcome	Added non-inferiority margin justification (2.8%): derived from 20% relative increase ($14\% \times 0.2 = 2.8\%$) and clinical acceptability	Address clinical relevance of margin required
V1.2	Subgroup analysis	Added subgroup by center volume: high-volume vs low-volume	Support comparison between high-and lowvolume centers
V1.2	Appendix	Added templates for statistical analysis tables	Standardized and formalized output.
